11.5 Removal of Subjects from Therapy or Assessments

Although the importance of completing the entire clinical study will be explained to the subjects, any subject is free to discontinue his/her participation in the study at any time and for whatever reason, specified or unspecified, and without any prejudice. No constraints are to be imposed on the subject, and when appropriate, a subject may be treated with other conventional therapy when clinically indicated once the subject is no longer in the study. Investigators or the sponsor can also withdraw subjects from the clinical study if deemed to be necessary.

Unless medically urgent, investigators are required to contact the Medical Monitor to discuss patients that are being considered for withdrawal from study drug treatment or from the study.

A subject may be withdrawn from the study treatment at any time for the following reasons:

- At the discretion of the investigator or the sponsor for safety, behavioral, compliance, or administrative reasons.
- Occurrence of AEs, including laboratory abnormalities, not compatible with the continuation of subject participation in the study, in the investigator's opinion, or unacceptable to the subject to continue, including but not limited to the following:
 - Serious immediate-type allergic manifestations including anaphylactic reaction;

- Serious new or worsening of asthma, or newly diagnosed asthma considered related to study drug administration;
- Diagnosis of a malignancy (except curatively treated in situ cervical carcinoma, squamous cell carcinoma [Bowen's disease] or basal cell carcinoma);
- Opportunistic infections such as but not limited to active TB and other infections whose nature or course suggest an immune-compromised or immune-suppressed status;
- Any serious infection or any severe infection requiring treatment with parenteral antibiotics or oral antibiotics/antivirals/antifungals for > 2 weeks considered related to study drug administration; or
- Confirmed COVID-19 infection (at least a temporary discontinuation is required, while suspected COVID-19 may be acceptable see Section 11.5.2).
- ALT or AST > 3 x ULN and TBL > 2 x ULN or INR > 1.5
- Pregnancy, for which discontinuation of study drug is mandated.
- Use of non-permitted systemic concurrent therapy (discussed and agreed upon with the investigator and medical monitor).
- Use of systemic rescue therapy, as specified in Table 4 of Section 12.5.2 and Section 12.5.1.2. (discussed and agreed upon with the investigator and medical monitor).

The main reason for withdrawal will be documented in the electronic case report form (eCRF). Subjects who have been randomized and treated will not be replaced by another subject.

Subjects who prematurely discontinue study drug and/or take rescue medication(s) will be encouraged to complete the scheduled study visits.

When a subject discontinues study drug, he/she will be fully assessed whenever possible, and followed according to guidelines presented in Section 13.2.1.

Reasonable efforts will be made to contact subjects who are lost to follow-up. These efforts must be documented in the subject's file.

The sponsor has the right to terminate the study at any time in case of SAEs or if special circumstances concerning the investigational product or the company itself occur, making further treatment of subjects impossible. In this event, the investigator(s) will be informed of the reason for study termination.

11.5.1 Pregnancy

The safety of nemolizumab in pregnant or lactating women has not been established.

Subjects will be instructed that known or suspected pregnancy occurring during the study should be confirmed and reported to the investigator. If a subject becomes pregnant, the investigator must withdraw the subject from the study without delay. The subject must not receive any further injection(s) of the study drug.

The investigator must:

- Follow the procedures for reporting/follow-up of a pregnancy within 24 hours (see Section 16.12.4) of receipt of the information.
- Complete as fully as possible the applicable Pregnancy Surveillance Form(s) (see Section 16.12.4).
- Monitor and record the progress of the pregnancy until its outcome. Contact the subject's regular physician (general practitioner or gynecologist) or hospital staff to obtain further details and ask for regular follow-up information.
- Provide tri-monthly updates until the final outcome of the pregnancy. If the subject can no longer be reached (lost to follow-up), documentation of the non-response/contact with two phone calls and a letter (certified with return receipt) is required.
- If the pregnancy leads to an abortion (i.e., voluntary abortion, spontaneous abortion, or therapeutic abortion), in utero death, or congenital anomaly, follow the procedure for declaration of/reporting an SAE (Section 16.12.2).

The investigator and sponsor should also be notified of pregnancy occurring during the study (and within 12 weeks [\pm 5 days] after the last dose of study drug) but confirmed after completion of the study. In the event that a subject is subsequently found to be pregnant after inclusion in the study, any pregnancy will be followed to term, and the status of mother and child will be reported to the sponsor after delivery.

Full details will be recorded on the withdrawal page (exit form), or an SAE report will be completed if the subject has completed the study. Pregnancy is not to be considered as an AE; however, it must be monitored and reported as described in Section 16.12.4.

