13.2.1 Early Termination Visit

Subjects who prematurely discontinue from the study should complete an early termination (ET) visit at the time of discontinuation. A follow-up/final visit is required 12 weeks after the last study drug administration.

Subjects who prematurely discontinue the study treatment will be asked to continue participation in the study and return for all remaining visits and assessments.

Participation will continue until the subject completes the final study visit or otherwise discontinues study participation.

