16.5 Pregnancy Testing

All WOCBP will have a serum pregnancy test performed at all visits. Pregnancy test results must be available prior to the administration of the study drug.

Subjects with a positive serum pregnancy test result at screening must not be enrolled.

Subjects with a positive serum pregnancy test result during the trial must discontinue treatment and but remain in the study for follow-up.

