16.12.4 Pregnancy Reporting

Any pregnancy occurring during clinical studies where the fetus could have been exposed to the study drug must be monitored until its outcome in order to ensure the complete collection of safety data. If a subject becomes pregnant, the investigator must:

1. Withdraw the subject from the clinical study. The subject must not receive any further injection of the study drug.
2. Complete as fully as possible the Pregnancy Surveillance Form - Part I: History and Start of Pregnancy. Send by fax along with the exit form within 24 hours of receipt of the information to the PPD [REDACTED]

PPD [REDACTED]
[REDACTED]
[REDACTED]

[figure not shown]
Note: Immediate pregnancy reporting is required by the investigator if it occurs during the clinical study or within 12 weeks (\pm 5 days) of receiving the last dose of study drug, whether or not the event is considered to be related to the investigational product.

3. Monitor and record the progress of the pregnancy until its outcome. Contact the subject's regular physician (general practitioner or gynecologist) or hospital staff to obtain further details and ask for regular follow-up information.
4. Provide tri-monthly updates until the final outcome of the pregnancy, by completing the Pregnancy Surveillance Form - Part II: Course and Outcome of Pregnancy. For all additional follow-up evaluations, send the form by fax to the PPD [REDACTED] within 24 hours of receipt of the information. If the subject can no longer be reached (i.e., lost to follow-up), documentation of the non-response/contact with two phone calls and a letter (certified with return receipt) is required.
5. At the outcome of the pregnancy, complete as fully as possible the Pregnancy Surveillance Form - Part II: Course and Outcome of Pregnancy. Print and send the form by fax to the PPD [REDACTED] within 24 hours of receipt of the information.
6. If the pregnancy leads to an abortion (i.e., voluntary abortion, spontaneous abortion, or therapeutic abortion), in utero death or congenital anomaly, follow the procedure for declaration/reporting an SAE (see Section 16.12.2).

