19.3.1 Analysis of Primary Efficacy Endpoint

Primary efficacy endpoint and related estimand are the following:

Primary Efficacy Estimand Description	Estimand Attributes
In adult hemodialysis patients with chronic kidney disease and associated moderate to severe pruritus, 2 nemolizumab dosing schedules ^[1] compared to placebo by the difference in proportions of responders where response is defined as an improvement from baseline of WI NRS ≥ 4 at Week 12 without use of rescue therapies and without treatment discontinuation due to lack of efficacy or AE/death related to study drug	
Treatment Conditions: initial dose of nemolizumab (60 mg) or placebo at baseline, then nemolizumab (30 mg or 60 mg) or placebo Q4W at Weeks 4 and 8 via subcutaneous injection.
 
Population: adult hemodialysis patients with chronic kidney disease and associated moderate to severe pruritus (will be estimated in the Intent-to-Treat analysis set).
 
Variable: a binary composite response where:
 
Responder is defined as an improvement ≥ 4 in WI NRS from baseline at Week 12 without use of rescue therapies and without treatment discontinuation due to lack of efficacy or AE/death related to study drug.
 
Non-responder is defined as an improvement < 4 in WI NRS from baseline at Week 12 or use of rescue therapies or treatment discontinuation due to lack of efficacy or AE/death related to study drug.
 
Strategies for Intercurrent Events: A composite strategy was chosen for the use of rescue therapies and treatment discontinuation due to lack of efficacy or AE/death related to study drug; in case of use of rescue therapies or treatment discontinuation due to lack of efficacy or AE/death related to study drug, subjects will be considered as treatment failures in the binary composite response. In the case of treatment discontinuation for any other reason, a treatment policy strategy will be used and observed after discontinuation data (if available) will be used.
 
Summary measure: treatment difference of nemolizumab from placebo in proportions of responders

[1] Dosing schedules compared to placebo Q4W are an initial SC dose of nemolizumab (60 mg) at baseline then either 30 mg or 60 mg Q4W at Week 4 and Week 8.

Abbreviation(s): WI NRS = Worst Itch Numeric Rating Scale; Q4W = Every 4 Weeks

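### Protocol 11.5.1 and 16.12.4 withdraw a pregnant subject from the study, while 16.5 keeps her in the study off drug

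*Protocol*

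**What the plan says.** Five places in the protocol bear on a subject who becomes pregnant after randomization.

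- **Section 11.5.1 (Pregnancy):** "If a subject becomes pregnant, the investigator must withdraw the subject from the study without delay". It bars further injections. On paperwork it adds: "Full details will be recorded on the withdrawal page (exit form), or an SAE report will be completed if the subject has completed the study".
- **Section 16.12.4 (Pregnancy Reporting):** the first step is "Withdraw the subject from the clinical study", with the exit form sent alongside the pregnancy form within 24 hours.
- **Section 16.5 (Pregnancy Testing):** a subject with a positive serum test during the trial "must discontinue treatment and but remain in the study for follow-up".
- **Section 11.5 (Removal of Subjects):** among the reasons for withdrawal from study treatment it lists "Pregnancy, for which discontinuation of study drug is mandated".
- **Section 13.2.1 (Early Termination Visit):** this gives two paths. Subjects who leave the study have an early termination visit, and then "A follow-up/final visit is required 12 weeks after the last study drug administration". For those who only stop drug: "Subjects who prematurely discontinue the study treatment will be asked to continue participation in the study and return for all remaining visits and assessments".

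**The concern.** Sections 11.5.1 and 16.12.4 order study withdrawal, and 16.5 orders the opposite. Both instructions are mandatory and one event can trigger both, because women of childbearing potential have a serum test at every visit. A site that follows one rule departs from the other.

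The choice matters in two ways.

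- **Safety observation.** Several things survive withdrawal: the early termination visit, the final visit 12 weeks after the last dose, the 12-week reporting of adverse events (16.9.4, 16.12.1, 16.12.2), and surveillance of the pregnancy to its outcome. Scheduled visits of an exposed pregnant subject can still be lost.
- **The primary estimand.** Section 11.5.1 says pregnancy is not an adverse event, and it is not lack of efficacy either. Stopping drug for it therefore falls into the residual category of Section 19.3.1: "In the case of treatment discontinuation for any other reason, a treatment policy strategy will be used", with post-discontinuation data used where available. Withdrawal before Week 12 can stop those data being collected and leave the value to multiple imputation.

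**Working it through.** **Is there a governing rule?** No figure in the plan is in dispute, so the first check is textual.

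| Section | Stop drug? | Stay in study? |
|---|---|---|
| 11.5 | Yes | Not stated; listed under withdrawal from treatment |
| 11.5.1 | Yes | No, exit form |
| 13.2.1 (general rule) | Already stopped | Yes, all remaining visits |
| 16.5 | Yes | Yes |
| 16.12.4 | Yes | No, exit form |

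Section 19 lets the SAP override the protocol where they differ, but SAP Section 12.3 covers only testing and a listing. The footnotes to the schedule of assessments, including the one on the pregnancy test, are blacked out in the public copy. I can therefore say only that no readable text ranks the instructions.

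**What can be lost.** Inputs:

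- Doses on Days 1, 29 and 57; later visits on Days 57, 85 and 141 (Protocol Table 5).
- Final visit after leaving the study = last dose day + 84 (13.2.1).
- Diary evening entries run to Day 140. The Week 12 window is Days 78 to 84 (SAP Table 4), extendable by five days at each end, to Days 73 to 89.

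| Found, before any dose due that day | Last dose | Final visit | Scheduled visits not matched | Diary days at risk | Of these, up to Day 84 |
|---|---|---|---|---|---|
| Week 4, Day 29 | Day 1 | 1 + 84 = Day 85 | Days 57 and 141 | 140 − 29 + 1 = 112 | 84 − 29 + 1 = 56 |
| Week 8, Day 57 | Day 29 | 29 + 84 = Day 113 | Days 85 and 141 | 140 − 57 + 1 = 84 | 84 − 57 + 1 = 28 |
| Week 12, Day 85 | Day 57 | 57 + 84 = Day 141 | None | 140 − 85 + 1 = 56 | 0 |

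The first two rows can lose the whole Week 12 window, including its extension. In all three rows the Week 4 window (Days 22 to 28) is already complete.

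SAP Table 3 assigns Days 71 to 113 to the Week 12 analysis visit for laboratory tests, vital signs and examinations. In the Week 4 row, the Day 85 final visit fills that slot. In the Week 8 row, a final visit on Day 113 fills it, but on the last permitted day. In both rows the Week 20 slot is empty, and in the Week 4 row so is Week 8.

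**Effect on the primary result.** Let y (0 or 1) be the response that would have been observed, and p the average imputed response. Losing the data shifts that arm's crude proportion by |y − p|/84, which is at most 1/84 = 0.0119, or 1.2 points. As an illustration, take p at the planning rates:

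- Nemolizumab, p = 0.5: 0.5/84 = 0.6 points.
- Placebo, p = 0.2: 0.2/84 = 0.2 points, or 0.8/84 = 1.0 point.

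The documents give no expected number of pregnancies. If one, two or three were lost in the same arm, the ceilings would be 1.2, 2.4 and 3.6 points.

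**The case against.** The strongest reply is that the conflict is narrower than it looks. Sections 11.5.1 and 16.12.4 are the dedicated pregnancy sections, they cross-refer, and they agree. The odd one out is a single sentence in a testing section. Section 13.2.1 is a general rule to which pregnancy could be an exception, and the item in 11.5 sits in a list about treatment, so it would name only study drug. Follow-up in 16.5 could mean follow-up of the pregnancy. A site might also stop drug on a positive test and withdraw on confirmation. Section 11.5 requires contact with the Medical Monitor before withdrawal unless it is medically urgent.

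These are possible readings, but the protocol states none of them. Section 16.5 says she remains in the study, and the other two sections order an exit form. Medical Monitor contact gives a site someone to ask, not a rule. It is fair that 11.5 and 13.2.1 add context rather than separate contradictions.

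On size, several points stand. The primary imputation uses data up to Week 12, so the relevant diary counts are 56 and 28 days, not 112 and 84. The analysis is defined either way, because missing values are imputed and then examined by copy-reference, non-responder and tipping-point analyses. Contraception requirements and exclusion of pregnancy at entry should keep numbers low. Amending 16.5 alone would also remove the contradiction, with fewer edits.

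**Conclusion.** The contradiction is real and lies in the current text of one protocol version. It is minor. The main consequence is for site conduct and for the scheduled follow-up of an exposed pregnant subject. The effect on the primary comparison is capped at 1.2 points of one arm's crude responder proportion per subject, and is negligible on the assumption that pregnancies are few. The diary losses are upper limits. They assume that diary collection ends on the day pregnancy is found, that she would otherwise have completed every entry, and that visits fall on their target days.

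The direction of the correction is more than taste. Sections 11.5, 13.2.1 and 16.5 are all consistent with stopping drug while staying in the study, and the treatment-policy strategy needs the data that this yields.

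**What to change.** In 11.5.1 and 16.12.4, replace withdrawal from the study with permanent discontinuation of study drug, continued participation under 13.2.1 and 16.5 if the subject agrees, and surveillance of the pregnancy to its outcome. Keep the 24-hour Pregnancy Surveillance Form. Change the exit-form wording in both sections so that the form is completed only if she leaves the study.

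If the sponsor does intend study withdrawal, 16.5 must say so, and the loss of post-discontinuation data should be accepted openly.

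The cost is wording in two sections, with no change to the analysis or sample size. Because it changes what sites do, the sponsor must decide whether it is an administrative or a substantial amendment under Section 20.7.1. It could travel with the next planned amendment, with a clarification to sites meanwhile.

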11.5.2 Coronavirus Disease 2019

Study drug administration will be discontinued in a subject in whom COVID-19 is confirmed or suspected. COVID-19 must be specified as the reason for study drug discontinuation.

Study drug administration may resume in subjects with confirmed or suspected COVID-19 based on investigator judgment after discussion with the medical monitor or Sponsor and only if the following minimum conditions are met:

- **For symptomatic subjects:** At least 14 days have passed since recovery, defined as resolution of fever without the use of fever-reducing medications and improvement in respiratory symptoms (e.g., cough, shortness of breath).
- **For asymptomatic subjects:** At least 21 days have passed since the positive PCR test and no symptoms.

Note: The above should be considered minimum criteria. Where the local guidelines are more stringent for infection resolution criteria, those must be applied.

See [Appendix 1](#) for additional guidance for management of subjects and study conduct during the COVID-19 pandemic.

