4.11.3 Per Protocol (PP) Set

The Per Protocol (PP) Set include all randomized subjects who receive all scheduled doses of study drug and have Baseline and Week 12 assessments of WI NRS and with no major deviation that could impact efficacy. The PP Set will be used for the supplementary analysis of the primary endpoint. Subjects will be summarized and analyzed according to their randomized treatment group.

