9.1.3 Impact of COVID-19 on the Primary Efficacy Endpoint (Estimand 1)

To assess the impact of COVID-19 related study disruptions (e.g. treatment discontinuation, missing assessments, etc.), the primary efficacy endpoint will also be analyzed on the ITT Set excluding subjects affected by COVID-19 related study disruptions. Missing values will be imputed using MI under MAR assumption (dichotomous endpoints will be calculated from the underlying imputed variable). Subjects affected by COVID-19 related study disruptions will not be included in the MI.

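### Protocol 11.5 appears to let study drug continue in suspected COVID-19, while 11.5.2, to which it refers, requires that it be stopped

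*Protocol*

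**What the plan says.** Protocol 11.5 lists reasons for taking a subject off study treatment. The list opens permissively: "A subject may be withdrawn from the study treatment at any time for the following reasons". One entry separates two COVID-19 cases: "Confirmed COVID-19 infection (at least a temporary discontinuation is required, while suspected COVID-19 may be acceptable see Section 11.5.2".

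Protocol 11.5.2, the section cited there, makes no such separation: "Study drug administration will be discontinued in a subject in whom COVID-19 is confirmed or suspected". It then deals with restarting, again for both cases together: "Study drug administration may resume in subjects with confirmed or suspected COVID-19 based on investigator judgment after discussion with the medical monitor or Sponsor". Minimum conditions follow. Symptomatic subjects must wait at least 14 days after recovery. For asymptomatic subjects the condition is: "At least 21 days have passed since the positive PCR test and no symptoms".

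Protocol 11.5.2 also refers to Appendix 1 for further COVID-19 guidance. The text of that appendix is redacted in the public document.

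**The concern.** A reader who follows the cross-reference in 11.5 to find out how a suspected case is handled arrives at an instruction that points the other way. The matter is whether a subject with possible COVID-19 receives the next injection. Protocol 8.4 names infections among the potential risks of nemolizumab, and Protocol 8.4 and 16.10 make confirmed and suspected COVID-19 adverse events of special interest. The handling of such a subject should not depend on which section the site happened to read.

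There is also a compliance side. A site that relies on wording found in 11.5 could be recorded as deviating from 11.5.2.

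On the analysis side, a withheld dose has defined consequences. The SAP's Per Protocol Set will "include all randomized subjects who receive all scheduled doses of study drug and have Baseline and Week 12 assessments of WI NRS". SAP 8.4.1 counts injections missed because of COVID-19. Under SAP 9.1.3, "the primary efficacy endpoint will also be analyzed on the ITT Set excluding subjects affected by COVID-19 related study disruptions".

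**Working it through.** No figure in the plan depends on this point, so the check is a comparison of text followed by a short look at the dosing calendar.

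**1. The two sections side by side**

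| Case | Protocol 11.5 | Protocol 11.5.2 |
|---|---|---|
| Confirmed | Interruption compulsory, at least for a time | Drug stopped |
| Suspected | Described as possibly acceptable, with a pointer to 11.5.2 | Drug stopped |
| Restarting | Not covered | Conditions set for confirmed and suspected cases together |

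The sections agree on confirmed infection and part only on suspected infection. The inclusion of suspected cases in 11.5.2 is not a slip of one word, because its restart rule covers them a second time.

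**2. What a site can do in a suspected case**

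- Stop drug: compatible with 11.5, whose list is permissive, and with 11.5.2.
- Continue drug: compatible with 11.5 on its natural reading, and a breach of 11.5.2.

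The conflict therefore bites only at sites that use the 11.5 allowance.

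**3. Restarting**

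A suspected symptomatic subject has a countable condition, since recovery can be dated without a test. A suspected asymptomatic subject who has not been tested does not, because the 21 days run from a positive PCR result.

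**4. When an interruption costs a dose**

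Inputs: injections on Days 1, 29 and 57, with a window of ±3 days at Weeks 4 and 8 (Protocol Table 5); waits of 14 and 21 days (Protocol 11.5.2); dosing outside the window allowed if at least three weeks have passed since the last injection (Protocol 12.3).

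- Asymptomatic with a positive PCR test: 29 − 21 = Day 8, so a test dated by Day 8 still allows the Week 4 injection on its target day. With the window, 32 − 21 = Day 11.
- Symptomatic: 29 − 14 = Day 15 for recovery, or 32 − 14 = Day 18 with the window.
- Beyond these days the injection is late, but Protocol 12.3 allows a late injection.

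The baseline injection is largely outside the issue, because exclusion criterion 10 bars confirmed or suspected COVID-19 within two weeks before screening or baseline.

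**5. Route into the analysis**

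The primary analysis uses the ITT Set (SAP 4.11.1). Under SAP Section 5, Table 5, stopping treatment for a reason other than lack of efficacy or a drug-related adverse event or death follows a treatment-policy strategy, with observed values used. A COVID-19 stop that is not judged drug-related thus changes exposure and does not by itself make the subject a non-responder. What remains open to influence is the missed-injection count, the Per Protocol Set (supplementary only, SAP 9.1.2) and the COVID-19 impact set.

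**The case against.** The strongest reply is that 11.5 does not state a second rule at all. Its phrase on suspected cases is elliptical: it never says what may be acceptable, and it defers to 11.5.2, which is specific and clear. The redacted Appendix 1 may settle the matter as well. This stands in part. That dosing may continue is the natural reading, given the contrast with what is required for confirmed cases, but it is not the literal text. The appendix could not be checked. Even so, a clause that sets suspected cases apart and then points to a section that treats them the same will mislead some readers, and no other readable text resolves it.

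A reader might infer that sites cannot comply with both sections. The documents do not support that, because stopping drug in every suspected case satisfies both.

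A reader might also infer that each interruption costs one of the three dosing visits and removes the subject from the Per Protocol Set. The calendar above shows otherwise: an episode can clear between visits, and a late injection is allowed.

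Finally, randomization is blinded and stratified by clinical site (Protocol 12.2; SAP 4.3), so differences between sites in handling suspected cases should fall about evenly across the arms. Adverse events of special interest are collected and a data monitoring committee reviews safety. These points limit the harm to the comparison. They do not tell a site what to do with the subject in front of it.

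**Conclusion.** The point holds in a limited form. Protocol 11.5 appears to permit continued dosing in suspected COVID-19, and 11.5.2 forbids it, so subjects with the same presentation may be treated differently at different sites. The restart rule in 11.5.2 also leaves an asymptomatic, untested suspected case without a start date.

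The weight lies in subject safety and consistent conduct. The effect on the analysis is secondary, arises only through doses actually missed, and cannot be sized, because the documents give no rate of suspected COVID-19. Two inferences go too far. One is that the primary result is at risk: the treatment-policy handling makes the effect there small, unless the infection is judged related to study drug. The other is that the SAP contradicts itself: its visible COVID-19 categories rest on disruptions and discontinuations attributed to COVID-19, and no inconsistency among them was found.

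The conclusion rests on the natural reading of the clause in 11.5 and on the readable text only. If Appendix 1 deals expressly with suspected cases, the practical risk is smaller, but the two body sections would still disagree.

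**What to change.** Protocol 11.5 and 11.5.2 must be reconciled into one statement for suspected infection. The same edit should say how resumption is timed for a subject who has no positive PCR test, and Appendix 1 should be checked against the result. Which rule applies is a clinical decision for the sponsor, and no view is offered here. The SAP needs no change on this account. The cost is a few lines in the next amendment or a clarification letter to sites.
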